8.2 Determination of Sample Size

It is anticipated that approximately 50 HCV infected, DAA treatment-experienced subjects who have experienced virologic failure in an AbbVie HCV parent study will be enrolled.

8.3 Randomization Methods

This study is not randomized. Eligible subjects will be allocated to a treatment arm according to their HCV genotype, cirrhosis status (presence/absence), and prior treatment experience with PI- and/or NS5Ai-containing regimens before experiencing virologic failure in the AbbVie HCV parent study.

9.0 Ethics

9.1 Independent Ethics Committee (IEC) or Institutional Review Board (IRB)

Good Clinical Practice (GCP) requires that the clinical protocol, any protocol amendments, the Investigator's Brochure, the informed consent and all other forms of subject information related to the study (e.g., advertisements used to recruit subjects) and any other necessary documents be reviewed by an IEC/IRB. The IEC/IRB will review the ethical, scientific and medical appropriateness of the study before it is conducted. IEC/IRB approval of the protocol, informed consent and subject information and/or advertising, as relevant, will be obtained prior to the authorization of drug shipment to a study site.

Any amendments to the protocol will require IEC/IRB approval and approval by Regulatory Authority(ies), if required by local regulations, prior to implementation of any changes made to the study design. The investigator will be required to submit, maintain and archive study essential documents according to ICH GCP and all other applicable regulatory authorities.

Any serious adverse events that meet the reporting criteria, as dictated by local regulations, will be reported to both responsible Ethics Committees and Regulatory Agencies, as required by local regulations. During the conduct of the study, the investigator should promptly provide written reports (e.g., ICH Expedited Reports, and any additional reports required by local regulations) to the IEC/IRB of any changes that affect the conduct of the study and/or increase the risk to subjects. Written documentation of the submission to the IEC/IRB should also be provided to AbbVie.

9.2 Ethical Conduct of the Study

The study will be conducted in accordance with the protocol, International Council on Harmonisation (ICH) guidelines, applicable regulations and guidelines governing clinical

study conduct and the ethical principles that have their origin in the Declaration of Helsinki. Responsibilities of the clinical investigator are specified in [Appendix A](#).

9.3 Subject Information and Consent

The investigator or his/her representative will explain the nature of the study to the subject, and answer all questions regarding this study. Prior to any study-related screening procedures being performed on the subject, the informed consent statement will be reviewed and signed and dated by the subject, the person who administered the informed consent, and any other signatories according to local requirements. A copy of the informed consent form will be given to the subject and the original will be placed in the subject's medical record. An entry must also be made in the subject's dated source documents to confirm that informed consent was obtained prior to any study-related procedures and that the subject received a signed copy.

The optional pharmacogenetic testing and analyses will only be performed if the subject has voluntarily signed and dated the IRB/IEC approved pharmacogenetic informed consent, after the nature of the testing has been explained and the subject has had an opportunity to ask questions. The pharmacogenetic informed consent must be signed before the pharmacogenetic testing is performed. If the subject does not consent to the additional pharmacogenetic testing, it will not impact the subject's participation in the study.

In the event a subject withdraws from the main study, optional pharmacogenetic exploratory research samples will continue to be stored and analyzed unless the subject specifically withdraws consent for the optional samples. If consent is withdrawn for the optional sampling, the subject must inform their study doctor, and once AbbVie is informed, the optional samples will be destroyed. However, if the subject withdraws his/her consent and the samples have already been tested, those results will still remain as part of the overall research data.

10.0 Source Documents and Case Report Form Completion

10.1 Source Documents

Source documents are defined as original documents, data and records. This may include hospital records, clinical and office charts, laboratory data/information, subjects' diaries or evaluation checklists, pharmacy dispensing and other records, recorded data from automated instruments, microfiches, photographic negatives, microfilm or magnetic media, and/or x-rays. Data collected during this study must be recorded on the appropriate source documents. The Investigator Awareness Date (SAE CRF) may serve as the source for this data point. This adverse event data point required for eCRF completion can be entered directly in the eCRF.

The investigator(s)/institution(s) will permit study-related monitoring, audits, IEC/IRB review, and regulatory inspection(s), providing direct access to source data documents.

10.2 Case Report Forms

Case report forms (CRF) must be completed for each subject screened/enrolled in this study. These forms will be used to transmit information collected during the study to AbbVie and regulatory authorities, as applicable. The CRF data for this study will be collected with an electronic data capture (EDC) system called Rave[®] provided by the technology vendor Medidata Solutions Incorporated, NY, USA. The EDC system and the study-specific electronic case report forms (eCRFs) will comply with Title 21 CFR Part 11. The documentation related to the validation of the EDC system is available through the vendor, Medidata, while the validation of the study-specific eCRFs will be conducted by AbbVie and will be maintained in the Trial Master File at AbbVie.

The investigator will document subject data in his/her own subject files. These subject files will serve as source data for the study. All eCRF data required by this protocol will be recorded by investigative site personnel in the EDC system. All data entered into the eCRF will be supported by source documentation.

The investigator or an authorized member of the investigator's staff will make any necessary corrections to the eCRF. All change information, including the date and person performing the corrections, will be available via the audit trail, which is part of the EDC system. For any correction, a reason for the alteration will be provided. The eCRFs will be reviewed periodically for completeness, legibility, and acceptability by AbbVie personnel (or their representatives). AbbVie (or their representatives) will also be allowed access to all source documents pertinent to the study in order to verify eCRF entries. The principal investigator will review the eCRFs for completeness and accuracy and provide his or her electronic signature and date to eCRFs as evidence thereof.

Medidata will provide access to the EDC system for the duration of the trial through a password-protected method of internet access. Such access will be removed from investigator sites at the end of the site's participation in the study. Data from the EDC system will be archived on appropriate data media (CD-ROM, etc.) and provided to the investigator at that time as a durable record of the site's eCRF data. It will be possible for the investigator to make paper printouts from that media.

11.0 Data Quality Assurance

To ensure data integrity and subject safety, a study monitor will continuously, throughout the study, verify that all subjects sign the informed consent prior to any study specific procedures being conducted, that the protocol procedures are being followed appropriately, and that the information provided in the eCRF is complete, accurate, and supported by information in source documents. Computer logic and manual checks will be created to identify items such as inconsistent study dates. Any necessary corrections will be made to the eCRF.

12.0 Use of Information

Any research that may be done using optional pharmacogenetic exploratory research samples from this study will be experimental in nature and the results will not be suitable for clinical decision making or patient management. Hence, the subject will not be

informed of individual results, should analyses be performed, nor will anyone not directly involved in this research. Correspondingly, researchers will have no access to subject identifiers. Individual results will not be reported to anyone not directly involved in this research other than for regulatory purposes. Aggregate data from optional pharmacogenetic exploratory research may be provided to investigators and used in scientific publications or presented at medical conventions. Optional pharmacogenetic exploratory research information will be published or presented only in a way that does not identify any individual subject.

13.0 Completion of the Study

The investigator will conduct the study in compliance with the protocol and complete the study within the timeframe specified in the contract between the investigator and AbbVie. Continuation of this study beyond this date must be mutually agreed upon in writing by both the investigator and AbbVie. The investigator will provide a final report to the IEC/IRB following conclusion of the study, and will forward a copy of this report to AbbVie or their representative.

The investigator must submit, maintain, and archive any records related to the study according to ICH GCP and other applicable regulatory requirements. If the investigator is not able to retain the records, he/she must notify AbbVie to arrange alternative archiving options.

AbbVie will select the signatory investigator from the investigators who participate in the study. Selection criteria for this investigator will include level of participation as well as significant knowledge of the clinical research, investigational drug and study protocol. The signatory investigator for the study will review and sign the final study report in accordance with the European Agency for the Evaluation of Medicinal Products (EMA) Guidance on Investigator's Signature for Study Reports.

The end-of-study is defined as the date of the last subject's last visit.

Appendix A. Responsibilities of the Clinical Investigator

Clinical research studies sponsored by AbbVie are subject to the Good Clinical Practices (GCP) and local regulations and guidelines governing the study at the site location. In signing the Investigator Agreement in Section 14.0 of this protocol, the investigator is agreeing to the following:

1. Conducting the study in accordance with the relevant, current protocol, making changes in a protocol only after notifying AbbVie, except when necessary to protect the safety, rights or welfare of subjects.
2. Personally conducting or supervising the described investigation(s).
3. Informing all subjects, or persons used as controls, that the drugs are being used for investigational purposes and complying with the requirements relating to informed consent and ethics committees (e.g., independent ethics committee [IEC] or institutional review board [IRB]) review and approval of the protocol and amendments.
4. Reporting adverse experiences that occur in the course of the investigation(s) to AbbVie and the site director.
5. Reading the information in the Investigator's Brochure/safety material provided, including the instructions for use and the potential risks and side effects of the investigational product(s).
6. Informing all associates, colleagues, and employees assisting in the conduct of the study about their obligations in meeting the above commitments.
7. Maintaining adequate and accurate records of the conduct of the study, making those records available for inspection by representatives of AbbVie and/or the appropriate regulatory agency, and retaining all study-related documents until notification from AbbVie.
8. Maintaining records demonstrating that an ethics committee reviewed and approved the initial clinical investigation and all amendments.

9. Reporting promptly, all changes in the research activity and all unanticipated problems involving risks to human subjects or others, to the appropriate individuals (e.g., coordinating investigator, institution director) and/or directly to the ethics committees and AbbVie.
10. Following the protocol and not making any changes in the research without ethics committee approval, except where necessary to eliminate apparent immediate hazards to human subjects.

Appendix C. Study Activities

Study Activities – Treatment Period

Activity	Screening	Day 1 ^a	Wk 2	Wk 4	Wk 8	Wk 12 (Arm B Only)	EOT/Premature D/C from Treatment ^b
Informed Consent ^c	X						
Medical History	X	X					
Physical Exam	X	X					X
Vital Signs, Weight, Waist Circumference, Height ^d	X	X	X	X	X	X	X
ECG	X						
Hematology/Chemistry/ Urinalysis/Coagulation Panel	X	X	X	X	X	X	X
Pregnancy Test (serum [s] urine [u]) ^e	X (s, u)	X (s, u)		X (u)	X (u)	X (u)	X (u)
FSH (all females)	X						
HBsAg, Anti-HIV Ab	X						
Hemoglobin A1c	X						
HCV Genotype and Subgenotype	X						
FibroTest/APRI or FibroScan [®] or Liver Biopsy ^f	X						
Total Insulin		X					X
Concomitant Medication Assessment	X	X	X	X	X	X	X
Adverse Event Assessment ^g	X	X	X	X	X	X	X
Study Drugs Dispensed		X		X	X	X	

Activity	Screening	Day 1 ^a	Wk 2	Wk 4	Wk 8	Wk 12 (Arm B Only)	EOT/Premature D/C from Treatment ^b
Study Drug Accountability and for Compliance			X	X	X	X	X
Dispense/Review Study Drug Dosing Card		X (Dispense only)	X	X	X	X	X (Review only)
HCV RNA Samples	X	X	X	X	X	X	X
HCV Resistance Sample		X	X	X	X	X	X
Archive Serum and Plasma Sample	X	X	X	X	X	X	X
Pharmacokinetic Samples ^h			X	X	X	X	X
Optional Pharmacogenetic Samples		X					
Child-Pugh Score ⁱ	X						X
Clinical Assessment of Hepatic Decompensation ^l		X					
HCC Screening: Liver Ultrasound ^l	X						
HIV-1 RNA ^j	X	X	X	X	X	X	X
Flow cytometry sample ^l	X	X				X	X

Wk = Week; EOT = End of treatment; D/C = Discontinuation

- All procedures to be performed prior to first dose.
- Subjects who prematurely discontinue the Treatment Period should return to the site to complete the Premature D/C Visit Procedures (preferably prior to the initiation of any other anti-HCV therapy).
- Subjects need to sign an IRB/IEC approved informed consent for the study (prior to performing any screening or study-specific procedures) and the optional pharmacogenetic sample(s), if applicable.
- Height will be measured at the Screening Visit only. Waist circumference will be measured at the Screening Visit, but if it is not measured at Screening, it may be measured on Day 1.

- e. Females not of CBP at Screening do not require pregnancy testing (Section 5.2.4).
- f. For subjects who were categorized as non-cirrhotic in the AbbVie parent study and have not had a qualifying liver biopsy within the previous 12 months or a qualifying FibroScan within the previous 6 months.
- g. See specific information regarding adverse event collection in Section 6.1.4.
- h. PK samples will be collected at each scheduled study visit except Day 1. Detail regarding timing of samples is provided in Section 5.3.2.1.
- i. Child-Pugh Score, Clinical Assessment of Hepatic Decompensation and Liver Ultrasound are only performed for subjects with compensated cirrhosis as described in Section 5.3.1.1.
- j. For HCV/HIV-1 co-infected subjects.

Study Activities – Post-Treatment (PT) Period

Activity	PT Wk 4	PT Wk 12	PT Wk 24 or PT D/C ^a
Vital Signs and Weight	X		
Hematology/Chemistry/Urinalysis/Coagulation Panel	X	X ^b	X ^{b,c}
Monthly Pregnancy Test (females) ^d	X (u)	X (u) (PT Weeks 8, 12, 16)	X (u) ^c
Concomitant Medication Assessment ^e	X	X	X
Adverse Event Assessment ^f	X	X	X
HCV RNA Samples	X	X	X
HCV Resistance Sample	X	X	X
Archive Serum and Plasma Sample	X	X	X
Optional Pharmacogenetic samples		X	
Child-Pugh Score ^g		X	X
HCC Screening: Liver Ultrasound ^g			X
HIV-1 RNA ^h	X	X	
Flow cytometry sample ^h	X	X	

Wk = Week; PT = Post-Treatment; D/C = Discontinuation

- Subjects who prematurely discontinue from the Post-Treatment Period should return to the site to complete the PT D/C Visit procedures.
- For the subjects enrolled with cirrhosis at Day 1. Chemistry and Coagulation Panel are required to calculate the Child Pugh Score.
- Hematology/Chemistry/Urinalysis/Coagulation Panel and Pregnancy Test are not required at PT Wk 24, but only at PT D/C if subject discontinued prior to PT Wk 4.
- Females not of CBP at Screening do not require pregnancy testing. Pregnancy testing should be completed every 4 weeks for 4 months after the last dose of RBV (or as directed per the local RBV label, whichever is more restrictive). At PT Weeks 8 and 16 subjects may have an unscheduled office visit for pregnancy testing or elect to perform the tests at home with test kits provided by the site. Additional testing may be required per local RBV label.
- Only medications taken for SAEs and for the treatment of HCV and HIV will be collected after 30 days post-dosing.

- f. Nonserious AEs and all SAEs will be collected until 30 days post dosing. Only SAEs will be collected thereafter, see Section 6.1.4.
- g. Required only for subjects with compensated cirrhosis as described in Section 5.3.1.1.
- h. For subjects with HCV/HIV-1 co-infected subjects.

Note: Day 1 of the Post-Treatment Period is defined as the day after the last day of study drug.

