- a. Also a component of the Child-Pugh Assessment (along with ascites and encephalopathy).
b. Only for known HCV/HIV-1 co-infected subjects.
c. Directly measured.
d. Performed only at Day 1.
e. Performed only at Screening.
f. Females not of CBP at Screening do not require pregnancy testing as defined in Section 5.2.1 Criterion 5.

Table 10. Clinical Laboratory Tests (Continued)

- g. Component of FibroTest and collected only if needed during the Screening Period.
- h. Performed for management of transaminase elevation (Section 6.1.7.5).
- i. Collected for confirmed Creatinine Clearance < 50 mL/min, if clinically indicated as defined in Section 6.1.7.6.

For any laboratory test value outside the reference range that the investigator considers to be clinically significant:

- The investigator will repeat the test to verify the out-of-range value.
- The investigator will follow the out-of-range value to a satisfactory clinical resolution.
- A laboratory test value that requires a subject to be discontinued from the study or requires a subject to receive treatment will be recorded as an adverse event.

The management of laboratory abnormalities that may occur during the study is described in Section 6.1.7.

Hepatitis B and HIV Screen

HBsAg (hepatitis B surface antigen) and anti-HIV Ab will be performed at Screening. The investigator must discuss any local reporting requirements to local health agencies with the subject. The site will report these results per local regulations, if necessary. The HBsAg results will be reported by the central laboratory to the clinical database.

Liver Diagnostic Testing

Subjects categorized as **cirrhotic** in the AbbVie HCV parent studies will be categorized as being cirrhotic in this study.

Subjects categorized as **non-cirrhotic** in the AbbVie HCV parent studies, who do not have a qualifying liver biopsy showing absence of cirrhosis within the previous 12 months from Screening or qualifying FibroScan showing absence of cirrhosis with the previous 6 months from Screening, but who otherwise meet all of the inclusion criteria and none of

the exclusion criteria will undergo liver biopsy or non-invasive testing (FibroTest/APRI or FibroScan) prior to enrollment. Selection of liver biopsy or non-invasive testing performed should be based on local standard practice.

Subjects must be documented as non-cirrhotic or cirrhotic defined as meeting one of the following criteria:

Non-Cirrhotic

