A liver biopsy within 12 months prior to or during Screening demonstrating the absence of cirrhosis, e.g., a METAVIR, Batts-Ludwig, Knodell, IASL, Scheuer, or Laennec fibrosis score of ≤ 3 , Ishak fibrosis score of ≤ 4 ; or

A FibroScan[®] score of < 12.5 kPa within ≤ 6 months of Screening or during Screening period (FibroScan[®] must be approved by the local regulatory agency to qualify for entrance criteria); or

A Screening FibroTest score of ≤ 0.48 and Aspartate Aminotransferase to Platelet Ratio Index (APRI) < 1 .

Cirrhotic

Previous histologic diagnosis of cirrhosis on liver biopsy, e.g., METAVIR, Batts-Ludwig, Knodell, IASL, Scheuer, or Laennec fibrosis score of > 3 , Ishak score of > 4 or on a liver biopsy conducted during Screening; or

A FibroScan[®] score of ≥ 12.5 kPa at any time prior to Screening or during Screening period (FibroScan[®] must be approved by the local regulatory agency); or

A Screening FibroTest result that is ≥ 0.75 and an APRI > 2 .

In the absence of a definitive diagnosis of presence or absence of cirrhosis by FibroTest/APRI using the above criteria (indeterminate FibroTest [$0.48 < \text{result} < 0.75$], or conflicting FibroTest and APRI results [e.g., FibroTest ≤ 0.48 , but APRI

≥ 1)), a liver biopsy or FibroScan[®] is required. Liver biopsy results will supersede Fibrotest/APRI or FibroScan[®] results and be considered definitive.

Subjects who are categorized as cirrhotic in this study according to the criteria above must also meet Inclusion Criteria 8 and 9.

When performed within the specified timeframes, the result of the liver biopsy supersedes the results of FibroScan and FibroTest/APRI and result of FibroScan supersedes the results of FibroTest/APRI.

Child-Pugh (Child-Turcotte-Pugh) Score and Category

The Child-Pugh (Child-Turcotte-Pugh) score uses five clinical measures of liver disease (3 laboratory parameters and 2 clinical assessments) as shown in [Table 11](#). Child-Pugh score will be determined only for subjects with compensated cirrhosis at the visits indicated in [Appendix C](#).

Table 11. Child-Pugh (Child-Turcotte-Pugh) Classification of Severity of Cirrhosis

Parameter	Points Assigned for Observed Findings		
	1	2	3
Total bilirubin, µmol/L (mg/dL)	< 34.2 (< 2)	34.2 – 51.3 (2 – 3)	> 51.3 (> 3)
Serum albumin, g/L (g/dL)	> 35 (> 3.5)	28 – 35 (2.8 – 3.5)	< 28 (< 2.8)
INR	< 1.7	1.7 – 2.3	> 2.3
Ascites*	None	Slight	Moderate to severe

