Note: For all windows, data must be on or before Study Drug End Day 2. The result closest to the scheduled time point will be used. Child-Pugh scores are only collected for subjects with compensated cirrhosis at the Screening Visit and End of Treatment Visit (Week 12 Visit for Arm A and Week 16 Visit for Arm B, or Premature Discontinuation Visit).

Table 5. Analysis Time Windows for HCV RNA and Resistance Endpoints (Post-Treatment Period)

Scheduled Visit ^a	Nominal Day (Study Drug End Day)	Time Window (Study Drug End Day Range)
Post-Treatment Week 4	28	3 to 56
Post-Treatment Week 12	84	57 to 126
Post-Treatment Week 24	168	127 to 999
SVR ₄ ^b	28	3 to 56
SVR ₁₂ ^b	84	57 to 126
SVR ₂₄ ^b	168	127 to 210

a. Post-Treatment Visits are applicable for subjects who received at least one dose of study drug.

b. For SVR windows, the last value in the window will be used.

Note: The result closest to the scheduled time point will be used, except for SVR₄, SVR₁₂, and SVR₂₄. For all windows, data must occur after Study Drug End Day 2. Study Drug End Day 0 is defined as the day of the last dose of study drug.

Table 6. Analysis Time Windows for Safety Laboratory and Vital Sign Measurements and Child-Pugh Score (Post-Treatment Period)

Scheduled Time ^a	Nominal Day (Study Drug End Day)	Time Window (Study Drug End Days Range)
Post-Treatment Week 4	28	3 to 56
Post-Treatment Week 12	84	57 to 126
Post-Treatment Week 24	168	127 to 999
Final Post-Treatment Visit ^a	> 2 days after last dose of study drug	

a. Post-Treatment Visits are applicable to subjects who received at least one dose of study drug.

b. The last value within the Post-Treatment Period window will be used to define the Final Post-Treatment value. The lower bound of this Final window is Study Drug End Day 3. Study Drug End Day 0 is defined as the day of the last dose of study drug.

Note: The result closest to the scheduled time point will be used. For all windows, data must occur after Study Drug End Day 2. Vital signs are collected at Post-Treatment Week 4 only; hematology, chemistry, urinalysis, and coagulation panels are collected at Post-Treatment Week 4 Visit or at Post-Treatment Discontinuation Visit if subject discontinues during the Post-Treatment Week 4 window. Child-Pugh scores are only collected for subjects with compensated cirrhosis at Post-Treatment Weeks 12, 24, and the Premature Discontinuation Visit.

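### No pregnancy test is specified at the post-treatment exit visit after PT Week 4, although testing is meant to run for 4 months after ribavirin

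*Protocol*

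**What the plan says.** The post-treatment table in protocol Appendix C has one column for PT Week 24 or PT D/C. Footnote a defines the exit visit: "Subjects who prematurely discontinue from the Post-Treatment Period should return to the site to complete the PT D/C Visit procedures".

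The pregnancy-test cell in that column carries footnote c, under which the laboratory "Panel and Pregnancy Test are not required at PT Wk 24, but only at PT D/C if subject discontinued prior to PT Wk 4". Footnote d covers the whole pregnancy-test row. It asks for tests every 4 weeks for 4 months after the last ribavirin dose, or as the local label directs if that is stricter. The Week 8 and Week 16 tests may be done at home or at an unscheduled visit. Section 5.3.1.1 (Pregnancy Testing) gives the same 4-month period, counted from the last study drug dose. The table places the post-treatment tests at Weeks 4, 8, 12 and 16.

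The laboratory-panel cell in the same column carries both footnotes b and c. Footnote b concerns subjects enrolled with cirrhosis and says "Chemistry and Coagulation Panel are required to calculate the Child Pugh Score". The Child-Pugh row is marked in that column under footnote g: "Required only for subjects with compensated cirrhosis as described in Section 5.3.1.1".

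The note to SAP Table 6 (Section 6.2) says that "coagulation panels are collected at Post-Treatment Week 4 Visit or at Post-Treatment Discontinuation Visit if subject discontinues" during the PT Week 4 window. It also says "Child-Pugh scores are only collected for subjects with compensated cirrhosis at Post-Treatment Weeks 12, 24, and the Premature Discontinuation Visit".

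**The concern.** Ribavirin is a known teratogen (protocol Section 3.0), which is why testing continues for months after the last dose. The PT D/C visit is the last planned contact with a subject who leaves early. Footnote c stops specifying a test at that contact from PT Week 4 on, while most of the testing period is still to come. A site working from the footnote could close out a woman of childbearing potential inside that period without a final test.

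The same footnote names the panel that supplies the Child-Pugh laboratory values and states no exception for cirrhosis. Read alone, it could lead a site to skip bloods that it needs for a required score.

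**Working it through.** The plan states no figure to reproduce. The check compares the footnotes.

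**Length of the testing period.** Four months is 4 × 365.25 / 12 = 121.75 days, and 121.75 / 7 = 17.4 weeks. The period therefore ends at about PT Week 17. This counts ribavirin and the other study drugs as stopping together. If ribavirin stopped earlier, the footnote d period ends earlier in the post-treatment schedule.

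**Footnotes c and d by time of exit.**

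| PT D/C visit | Footnote c | Footnote d | Result |
|---|---|---|---|
| Before PT Week 4 | Test required | Within period | Consistent |
| PT Week 4 to about Week 17, no test due that day | Not required | Within period, but no exit test stated | Gap |
| Same span, when the Week 8, 12 or 16 test is due | Not required | Test due | Contradiction |
| After about Week 17, or PT Week 24 itself | Not required | Period over | Consistent, unless the local label extends testing |

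The mismatch is confined to the two middle rows. As an example, a woman tested at Week 8 who attends PT D/C at Week 11 has no test specified at that visit. If she attends at Week 12, footnote d calls for a test and footnote c says none is required.

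**Footnotes b and c (laboratory panel).** Child-Pugh has 5 components, of which 3 are laboratory values: bilirubin, albumin and INR (protocol Table 11). Table 10 marks those tests with the note "Also a component of the Child-Pugh Assessment (along with ascites and encephalopathy". Section 5.3.1.1 says "Child-Pugh score will be determined only for subjects with compensated cirrhosis at the visits indicated in" Appendix C, and the Child-Pugh row is marked at PT Week 24 or PT D/C with no waiver attached. If footnote c overrode footnote b, then b would do nothing at PT Week 24 or at any exit from PT Week 4 on. The score would still be required without 3 of its 5 inputs. Both footnotes have effect only if b keeps chemistry and coagulation for cirrhotic subjects and c releases everyone else.

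**SAP.** The Table 6 note also leaves out cirrhotic bloods at PT Week 12, where the protocol cell carries footnote b alone and is unambiguous. The note is therefore an incomplete description and does not show which footnote prevails. The Table 6 windows would capture any bloods drawn, and the only Child-Pugh summary that the SAP describes is at baseline (Section 7.1).

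**The case against.** The strongest defence is that footnotes c and d do different jobs. Footnote d sets a monthly schedule and does not ask for a test at exit, so declining to specify one does not in general contradict it. Footnote c also has a sensible rationale. A woman who leaves before PT Week 4 has had no post-treatment test. One who leaves later has had the Week 4 test and, if on schedule, was tested within about the last 4 weeks. Contraception is required for at least 4 months after the last dose (Sections 5.2.4 and 6.1.6), and pregnancy information is collected for the duration of the study (Section 6.1.6).

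Most of this stands. There is no general conflict between c and d, only a gap and a contradiction when the visit coincides with a due test. A reader might also infer that women go untested from PT Week 4 on, or that footnote c causes the remaining monthly tests to be lost. The documents support neither. Tests stay scheduled at Weeks 8, 12 and 16. Any tests missed after exit would follow from leaving the study, and one exit test would not replace them.

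On the laboratory panel, a reader might infer that the protocol waives the Child-Pugh bloods in cirrhotic subjects. The double footnote marking and the required Child-Pugh row show otherwise, so only the wording needs attention.

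The defence does not explain why the exit-visit cutoff sits at PT Week 4 when the protocol's own testing period runs for 4 months.

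**Conclusion.** The point holds in a narrow form. Between PT Week 4 and about PT Week 17, footnote c specifies no pregnancy test at the exit visit of a woman of childbearing potential, although she is still within the testing period. When that visit coincides with a due test, c and d disagree.

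The effect is minor and limited to safety follow-up. SVR12 and the other efficacy results are unaffected. Planned enrolment is about 50 subjects, and the documents do not give the number of women of childbearing potential, of subjects with cirrhosis, or of early leavers, so the number affected cannot be estimated. The laboratory-panel issue is a secondary clarification of an evident intent. Waiving the pregnancy test at PT Week 24 itself agrees with footnote d unless a local ribavirin label extends testing that far. Overall this is a cheap improvement.

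**What to change.** 1. In footnote c, replace the PT Week 4 cutoff for the pregnancy test. Require a urine test at PT D/C for any woman of childbearing potential who exits within the footnote d period, or within a longer period set by the local ribavirin label. The cost is one urine test at a visit already held.
2. Add to footnote c: *except chemistry and coagulation for subjects with cirrhosis (footnote b)*. Because this states what the table already intends, it adds no planned procedure. Blood is drawn at that visit for HCV RNA in any case.
3. Optionally, align the SAP Table 6 note by listing chemistry and coagulation for subjects with cirrhosis at PT Week 12, PT Week 24 and PT D/C. This changes no analysis.
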